11 STUDY CALENDAR

See Appendix B for study evaluation calendar.

11.1 On Study Protocol Evaluation

11.1.1 Pre-treatment Evaluation: Pre-treatment tests should be performed within 8 weeks prior to enrollment on the trial unless otherwise stated. The evaluation required prior to starting treatment is listed in table form in Appendix B. The evaluation may be performed as part of enrollment onto NIH Protocol #04-C-0281 entitled: "Prospective Assessment of Clinical and Biological Factors Determining Outcomes in Patients with Chronic Graft-Versus-Host Disease". Attempts will be made to enroll patients on this study.

- 1. History and Physical Examination:** All patients should have a complete history (including prior and concurrent therapy) and physical examination including documentation and scoring of cGVHD, performance status, and signs and symptoms. Height, weight and body surface area must be recorded. All physical exam and cGVHD findings should be recorded and documented as per Appendices D-H. This evaluation should be within 2 weeks of starting therapy.
- 2. Hematology:** PT/PTT, fibrinogen, complete blood counts, with differential and platelet count. To be performed within 72 hours prior to starting therapy. If there is significant change in clinical status, all eligibility labs will be repeated prior to starting therapy.
- 3. Chemistries:** Electrolytes (including sodium, potassium, chloride, CO₂, calcium, phosphorus and magnesium), creatinine, BUN, glucose, SGOT, alkaline phosphatase, SGPT, and bilirubin. Serum iron studies (Fe, ferritin, and transferrin). To be performed within 72 hours prior to starting therapy. If there is significant change in clinical status, all eligibility labs will be repeated prior to starting therapy. For patients with serum creatinine levels above the age-adjusted normal limits, a 24 hour urine collection for creatinine clearance and eGFR will be performed.

4. Other lab tests: Infectious disease screening for CMV, HSV, EBV, HIV, HTLV, HBV, HCV, VZV, Lymphocyte Phenotyping TBNK and immunoglobulin levels. Research labs as defined in section 9.1.
5. Urine or Serum Pregnancy test: For all females of childbearing potential. This test is to be performed within 7 days prior to enrollment on the trial.
6. Pulmonary Function Tests (PFTs): All patients. Patients requiring a pediatric PFT lab will be evaluated by Children's National Medical Center (CNMC) Department of Pulmonology. Calculate lung function score (LFS) based on findings (Appendix O),
7. Radiographic Evaluation:
 - a. An MRI scan of one involved sclerotic skin area will be performed. The area will be determined based on severity of involvement and ability to adequately image after discussion between relevant study investigators. MRI will not be required for patients with contraindications to MRI procedure. (See section 3.5.4). Children who require sedation for MRI will be excluded.
 - b. All patients: High resolution CT scan of the chest following NIH Department of Radiology protocol for evaluation of bronchiolitis obliterans.
8. Evaluation by Ophthalmology for ocular cGVHD assessment, if indicated.
9. Evaluation by Dental Clinic for oral cGVHD assessment, if indicated.
10. Evaluation by Physiatry for ROM and functional status, includes occupational therapy (OT) assessment (Appendix S) will be performed within 2 weeks of starting therapy.
11. Evaluation by Dermatology for GVHD assessment of the skin will be performed within 2 weeks of starting therapy. A 6mm skin biopsy will be performed from an area of clinically affected skin in patients 18 years and older. This specimen will be divided for histological analysis and phospho-PDGFR studies.
12. Cardiac Evaluation: Baseline ECG and an echocardiogram or MUGA scan should be performed on all patients.
13. Quality of Life (QOL) and Functional Assessment (Appendices J-L, S): Patient-reported functional status measures include the Lee Symptom scale (Appendix K) and GVHD symptom self-assessment (Appendix L).
14. Leukapheresis (Optional): Collection of blood cells for research purpose only by a leukapheresis procedure - patient will have a consent option to decline. One pass leukapheresis will be performed in the Department of Transfusion Medicine (DTM) using standard procedure. Approximately 2-5 liters will be processed, with the goal to obtain approximately 2×10^9 cells per procedure. Leukapheresis will be offered only to subjects older than 18 years of age. The cells collected during this procedure will be used for Immune function, TGF- β , and IL-13 studies, as described in section 9.1.

11.1.2 On Study Evaluation:

1. History and physical examination, performance status at least once every other week for one month and once monthly while on treatment.
2. Laboratory Assessment (weekly for one month, every other week for 6 months and then approximately monthly thereafter): Complete blood count, differential and platelet count, electrolytes, creatinine, calcium, magnesium, phosphorus, SGPT, SGOT, bilirubin,

and routine infectious disease surveillance as clinically indicated. For patients with serum creatinine levels above the age-adjusted normal limits, an eGFR will be performed.

3. Urinalysis and Lymphocyte Phenotyping TBNK will be performed every 3 months.

4. Complete GVHD evaluation at the NIH will be performed every 3 months. This includes eye evaluation, dermatology assessment, oral assessment, ROM physiatry evaluation, pulmonary function tests (PFTs) if indicated, quality-of-life scales and functional assessment evaluation (including OT evaluation). NIH subspecialty exam (ie. ophthalmology, dentistry) will be employed if clinically indicated. ROM evaluation constitutes the primary study endpoint.

5. Research labs as per appendix C.

11.1.3 End of Study Evaluation:

The following tests and procedures should be performed, if possible, at the time a patient comes off treatment regardless of the reason for coming off treatment, unless the test or procedure has been performed in the last 4 weeks (2 weeks for physical examination and laboratory assessment). This evaluation should be at the NIH.

1. History and physical examination, performance status, ROM and functional assessment, and complete assessment of cGVHD including evaluation by Dermatology, Physiatry, and OT. Other evaluations such as Ophthalmology and Dental if indicated.
2. Laboratory Assessment: Complete blood count, differential and platelet count, Electrolytes, creatinine, calcium, magnesium, phosphorus, SGPT, bilirubin, and urinalysis.
3. MRI of the skin.
4. Pulmonary function tests (if indicated).
5. High resolution CT scan of the chest for patients with BO.
6. Quality-of-Life Scale.
7. Apheresis. (Optional)

At the physician's discretion, patients may be asked to return to the NIH for a one year off treatment evaluation prior to their removal from this study.

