3 PATIENT SELECTION

3.1 Eligibility Criteria

- 3.1.1 ScGVHD manifesting after at least 100 days following allogeneic hematopoietic stem cell transplantation is considered diagnostic for cGVHD according to NIH cGVHD Consensus Statement diagnostic criteria [10,13]. The diagnosis can be made clinically or by histopathology. The diagnosis must be confirmed by the principal investigator (PI), or lead associate investigator (LAI). Skin biopsies will be reviewed by the NCI Laboratory of Pathology to confirm the diagnosis of ScGVHD.
- 3.1.2 Patients must have measurable limitation in range of motion, defined as ScGVHD with or without fasciitis, restricting range of motion (ROM) of at least one joint with a minimum deficit of 25%. See Section 11 for the evaluation of measurable disease.
- 3.1.3 Prior therapy: Patients must have cGVHD refractory to at least one treatment regimen for cGVHD. One prior regimen must have included systemic corticosteroids at the equivalent prednisone dosing of 1mg/kg/day x 14 days. Patients in whom calcineurin inhibitors or

corticosteroids are medically contraindicated may also be eligible for enrollment. Patients who have had stabilization of disease on calcineurin inhibitors or steroids, but in whom these medications cannot be tapered without disease flare are also eligible. Patient must be on stable or tapering immunosuppressive regimen for at least one month.

- 3.1.4 Age: 4 years of age or older at the time of enrollment. Lower age limit set by lower established age limit norms of ROM scores for measurement criteria.
- 3.1.5 Life expectancy of greater than 6 months.
- 3.1.6 Karnofsky $\geq 60\%$; see Appendix A.
- 3.1.7 Patients must be platelet transfusion and growth factor independent at the time of study entry. Patients must have adequate organ and marrow function as defined below. Patients with Gilbert syndrome are excluded from the requirement of a normal bilirubin. (Gilbert syndrome is found in 3-10% of the general population, and is characterized by mild, chronic unconjugated hyperbilirubinemia in the absence of liver disease or overt hemolysis).

- X absolute neutrophil count $\geq 1,000/\text{mcL}$
- X platelets $\geq 50,000/\text{mcL}$
- X total bilirubin $< 3x$ upper limit of normal
- X AST(SGOT)/ALT(SGPT) $< 5 x$ upper limit of normal
- X creatinine age-adjusted within normal limits

OR

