creatinine clearance $\geq 30 \text{ mL/min/1.73 m}^2$ for adults and pediatric patients with BSA $\geq 0.97 \text{ m}^2$ with creatinine levels above institutional normals and $\geq 40 \text{ mL/min/1.73 m}^2$ for pediatric patients with BSA $< 0.97 \text{ m}^2$

Age (Years)	Maximum Serum Creatinine (mg/dL)
< 5	0.8
5 < age < 10	1.0
10 < age < 15	1.2
>15	1.5

- 3.1.8 Normal cardiac function for age as determined by ECHO or MUGA (normal LV function as measured by ejection fraction or shortening fraction).
- 3.1.9 The effects of imatinib mesylate on the developing human fetus at the recommended therapeutic dose are unknown. For this reason, women of child-bearing potential and men must agree to use adequate contraception (hormonal or barrier method of birth control; abstinence) prior to study entry, for the duration of study participation, and for six months following completion of therapy. Should a woman become pregnant or suspect she is pregnant while participating in this study, she should inform her treating physician immediately.
- 3.1.10 Ability to understand and the willingness to sign a written informed consent document. All patients or their legal guardian (for patients <18 years old) must sign an IRB approved document of informed consent (cGVHD natural history or any NCI protocol allowing for screening procedures) prior to performing studies to determine patient eligibility. After confirmation of patient eligibility all patients or their legal guardian must sign the protocol-specific informed consent. Pediatric patients will be included in age appropriate discussions and age appropriate assent will be obtained in accordance with NIH guidelines.
- 3.1.11 Durable Power of Attorney (DPA): All patients 18 years of age at the time of enrollment will be offered the opportunity to assign DPA so that another person can make decisions about their medical care if they become incapacitated or cognitively impaired.

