5 TREATMENT PLAN

5.1 Imatinib Mesylate Administration

This is an open-label pilot study of oral imatinib mesylate for ScGVHD. Adult patients will receive 100 mg imatinib mesylate daily and pediatric patients will be dosed at 65 mg/m² daily (100 mg maximum) for 28 days. If tolerated, after 28 days, adult patients will be increased to 200 mg daily and pediatric patients will be increased to 130 mg/m² (200 mg maximum). If the 100mg (or 65mg/m²) dose is not tolerated due to unacceptable toxicity within the first 28 days despite following the dosing delay guidelines (section 6.0), the drug will be discontinued, except for patients taking 100mg daily who are also on potent CYP3A4 inhibitors. This group will be allowed dose reduction to 50mg. Children with a BSA < 0.97 (starting dose 50mg) who do not tolerate the drug during the first 28 days will be taken off study because dose reduction below 50mg is not possible with the 100mg tablets. Treatment cycles are continuous 28-day cycles with no rest period between cycles.

Imatinib mesylate is supplied as 100 mg tablets. Adult patients will initially receive 100 mg imatinib mesylate daily and pediatric patients will be dosed at 65 mg/m² daily (100 mg maximum, see nomogram below). After 1 month, adult patients will increase to 200 mg daily and pediatric patients will receive 130 mg/m² daily. Individual patient dosages will be rounded to the nearest 50 mg increment. Tablets are scored and the 100 mg tablets may be cut into achieve 50 mg dosing. According to the package insert, tablets may be dispersed in a glass of water or apple juice, stir until disintegrated and administer immediately. Since no long-term stability data are available, the administration of imatinib suspension should not be delayed. Patient should take drug with a meal and a large glass of water (patients who dissolve their tablets in liquid do not need to drink additional water). See Appendix Q for patient instructions.

The product labeling for imatinib mesylate provides dosing guidelines for patients with renal dysfunction, as defined by the following criteria (Prod Info GLEEVEC® oral tablets, 2010):

Renal Dysfunction Definitions (based on Product labeling)

Mild CrCL = 40-59 mL/min

Moderate CrCL = 20-39 mL/min

Severe CrCL = <20 mL/min

Mild renal dysfunction

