The product labeling cautions that dose reduction may be needed at higher dosages of imatinib mesylate for patients with mild renal dysfunction. However, because patients on this protocol receive a low starting dose (100mg), dose adjustment will not be made for patients with mild renal dysfunction (creatinine clearance ≥ 40 ml/min).

Moderate renal dysfunction

As recommended by the product labeling guidelines (Prod Info GLEEVEC® oral tablets, 2010), patients with moderate renal dysfunction will decrease the starting dose by 50%. Therefore, adult patients and pediatric patients with BSA ≥ 0.97 will initially receive 50mg imatinib mesylate daily. After 1 month, adult patients and pediatric patients with BSA ≥ 0.97 and moderate renal dysfunction will increase to 100 mg daily if tolerated. Treatment and dose reductions will be based on estimated glomerular filtration rate (eGFR) and not on serum creatinine for patients with moderate renal dysfunction.

Children with a BSA < 0.97 (normal starting dose 50mg) with moderate renal dysfunction (creatinine clearance 30 -39ml/min) are ineligible because dose reduction is not possible below 50 mg.

Adult and pediatric patients with renal dysfunction between 20-30ml/min and with severe dysfunction (<20 ml/min) are not eligible for treatment.

Dose Nomogram for Pediatric Patients

65 mg/m ² /d		130 mg/m ² /d	
BSA [m²]	Dose [mg]	BSA [m²]	Dose [mg]
		0.38 – 0.57	50
0.58 – 0.96	50	0.58 – 0.96	100
≥ 0.97	100	0.97 – 1.34	150
		≥ 1.35	200

Patients receiving concomitant CYP3A4 inducers will have the starting dose of imatinib increased by 50%. The starting dosing of imatinib will be 150 mg/day for adult patients and 100 mg/m²/day for pediatric patients on concomitant CYP3A4 inducers. According to the package insert, tablets may be dispersed in a glass of water or apple juice, stir until disintegrated and administer immediately. Patients receiving concomitant CYP3A4 inhibitors (itraconazole, ketoconazole, posaconazole, voriconazole and fluconazole) will be monitored closely for toxicity, but routine dose reduction will not be employed.

Treatment will be administered on an outpatient basis. Reported adverse events and potential risks are described in Section 7. Appropriate dose modifications for imatinib mesylate are described in Section 6. No investigational or commercial agents or therapies other than those described below may be administered with the intent to treat the patient's cGVHD.

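### Section 5.1 sets the adult dose by renal clearance, but clearance or eGFR is required only when serum creatinine is raised, so some older or small women near 1.5 mg/dL could start at double the assigned dose

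*Combined protocol and SAP*

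**What the plan says.** Dose is tied to clearance. Section 5.1 defines the middle band as "Moderate CrCL = 20-39 mL/min" and states that "patients with moderate renal dysfunction will decrease the starting dose by 50" per cent. For adults this means 50 mg, rising to 100 mg after a month if tolerated; at 40 mL/min or above there is no adjustment. The bottom of the band is then removed: "Adult and pediatric patients with renal dysfunction between 20-30ml/min and with severe dysfunction (<20 ml/min) are not eligible for treatment". The working adult band is therefore about 30-39. For patients in it, Section 5.1 adds: "Treatment and dose reductions will be based on estimated glomerular filtration rate (eGFR) and not on serum creatinine".

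Testing is tied to serum creatinine. Section 3.1.7 admits a patient either with "creatinine age-adjusted within normal limits" or, for those "with creatinine levels above institutional normals", on a clearance of at least 30 mL/min/1.73 m² (adults). Its table puts the limit above age 15 at 1.5 mg/dL for both sexes. Section 11.1.1 item 3 then reads: "For patients with serum creatinine levels above the age-adjusted normal limits, a 24 hour urine collection for creatinine clearance and eGFR will be performed". Section 11.1.2 item 2 sets the same trigger for eGFR on study, and Appendix B asks for the 24-hour collection only when creatinine is elevated. No section requires an estimate for a patient whose creatinine is within the limit.

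**The concern.** The dose rule and the test trigger use different scales. Clearance at a given creatinine falls with age, is lower in women, and is lower at small body size, so one limit of 1.5 mg/dL cannot match a cut at 40 for everyone. A woman just inside the limit can be in the half-dose band without anything in the plan revealing it.

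She would then receive twice the assigned dose at both steps. The plan gives some reason to care. Section 2.1 notes that side effects are related to dose intensity. Section 14.1.1 reports that none of the 8 patients in the first cohort tolerated 400 mg. Section 5.1 allows azole CYP3A4 inhibitors without routine dose reduction. It also discontinues an adult who cannot tolerate 100 mg in the first 28 days, unless on a potent CYP3A4 inhibitor, whereas this patient should have begun at 50 mg. There is no upper age limit, and Section 2.2 mentions severe wasting, so older or low-weight patients are plausible.

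**Working it through.** The plan calculates no clearance and names no equation, so there is no stated figure to reproduce. The question is whether creatinine at or below 1.5 mg/dL can coexist with a value below 40.

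**Inputs from the plan:** dose cut at 40 and floor at 30 (Section 5.1); limit of 1.5 mg/dL above age 15 (3.1.7); at most 13 patients in the 200 mg cohort (14.1.1).

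**Assumed equations** (S = creatinine in mg/dL; forms for women with S above 0.7):
- Weight-based clearance (Cockcroft-Gault): (140 − age) × kg / (72 × S) × 0.85, in mL/min. Indexed: × 1.73/BSA, with BSA = √(kg × cm/3600).
- MDRD (175 version): 175 × S^−1.154 × age^−0.203 × 0.742.
- CKD-EPI 2009: 141 × (S/0.7)^−1.209 × 0.993^age × 1.018.
- CKD-EPI 2021: 142 × (S/0.7)^−1.200 × 0.9938^age × 1.012. This postdates the protocol version and serves only to widen the range.

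The last three use no weight and are in mL/min/1.73 m².

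**Example: woman, 60 years, 55 kg, 160 cm, creatinine 1.5 mg/dL (not above the limit)**
- Weight-based: 80 × 55 / (72 × 1.5) × 0.85 = 34.6.
- Indexed: BSA = √(55 × 160/3600) = 1.56; 34.6 × 1.73/1.56 = 38.3 (unrounded inputs).
- MDRD: 175 × 0.6263 × 0.4355 × 0.742 = 35.4.
- CKD-EPI 2009: 141 × 0.3980 × 0.6561 × 1.018 = 37.5.
- CKD-EPI 2021: 142 × 0.4007 × 0.6886 × 1.012 = 39.6.

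All are below 40. The last lies between the printed bands, which end at 39 and resume at 40.

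**How quickly the gap closes: women aged 60, weight-free equations**

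| Creatinine (mg/dL) | MDRD | CKD-EPI 2009 | CKD-EPI 2021 |
|---|---|---|---|
| 1.5 | 35.4 | 37.5 | 39.6 |
| 1.4 | 38.4 | 40.7 | 43.1 |
| 1.3 | 41.8 | 44.6 | 47.1 |
| 1.2 | 45.8 | 49.1 | 51.8 |

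Creatinine at which a woman's value equals 40, in the same order:
- age 50: 1.39, 1.51, 1.57
- age 60: 1.35, 1.42, 1.49
- age 70: 1.31, 1.34, 1.41

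At exactly 1.5 mg/dL a woman falls below 40 from age 33, 51 or 59, depending on the equation.

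**Body size (woman aged 60, 160 cm), weight-based value equal to 40:**
- indexed: 1.37 mg/dL at 50 kg, 1.44 at 55 kg, 1.50 at 60 kg
- unindexed: 1.18, 1.30 and 1.42

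**Men at 1.5 mg/dL:** the weight-free equations still give 44.5, 41.8 and 45.3 at age 85. Only the unindexed weight-based estimate falls below 40, at weights under 40 × 72 × 1.5/80 = 54.0 kg (age 60) or 40 × 72 × 1.5/70 = 61.7 kg (age 70).

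**The case against.** The strongest reply is that creatinine first, then clearance if raised, is a reasonable two-step screen used consistently throughout the plan, so only the position of the trigger is in dispute. That is largely right: the point is a mismatch at the edge of the limit, and a reader should not infer that screening on creatinine is unsound.

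Second, 3.1.7 also refers to institutional normals. If staff used a laboratory limit near 1.2 mg/dL, weight-free eGFR would miss no woman aged 60 (45.8-51.8) or 70 (44.4, 45.8, 48.7). This stands as a real qualification. However, 11.1.1 and 11.1.2 refer to age-adjusted limits, and the only ones the plan gives are in the table.

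Third, the window is narrow and depends on the equation. This also stands: at age 60 and 1.4 mg/dL only one of three weight-free equations is below 40, and at 1.3 none is.

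Fourth, the consequence is small. Section 5.2.4 forgoes routine reduction with listed CYP3A4 inhibitors because 100-200 mg is low against the usual 400 mg. Laboratory tests are weekly for a month and then every other week for 6 months, and the Section 6.1 toxicity rules apply. The footnote to the 6.1 table even places a patient classed as having normal renal function under the stricter rule for an eGFR toxicity. These safeguards stand, with one limit: on-study eGFR has the same creatinine trigger, so a stable 1.4-1.5 mg/dL never prompts it.

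Investigators may calculate eGFR anyway. The point concerns only what is required.

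**Conclusion.** The point holds as a minor dosing-safety gap. Followed as written, the plan can start some older or small women with creatinine of about 1.35-1.5 mg/dL at 100 then 200 mg when Section 5.1 assigns 50 then 100 mg. This rests on the assumed equations and on reading the trigger as 1.5 mg/dL. The size of the group depends on the equation and cannot be estimated from the documents.

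Three stronger readings are not supported:
- A reader might infer that the 8-of-10 tolerability rule is compromised. Nothing in the documents shows how many patients, if any, would be misclassified, so no effect on that rule is shown.
- A reader might infer that patients below the floor of 30 would commonly enter on creatinine. A woman aged 65, 50 kg, at 1.5 mg/dL is at 29.5 by the unindexed estimate, but at 34.9, 36.2 and 38.4 by the weight-free equations. This depends on the formula.
- A reader might extend the point to men or children. Men are missed only at low weight and only by the unindexed estimate. The check covers adults, and nothing here shows a gap for children.

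**What to change.** Adults only:

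1. In 11.1.1 item 3, 11.1.2 item 2 and Appendix B, calculate eGFR for every adult from recorded creatinine, age and sex, at eligibility and with each scheduled creatinine. Name one equation, for example a CKD-EPI version, in mL/min/1.73 m² to match the unit in 3.1.7.
2. Apply the Section 5.1 bands to that eGFR whatever the serum creatinine: below 40, 50 then 100 mg; below 30, not eligible. Writing "below 40" also closes the gap between 39 and 40.
3. Keep the 24-hour collection for raised creatinine. If it is also done in others, state that eGFR governs, in line with Section 5.1.
4. Add to 3.1.7 that an adult admitted on creatinine alone must also have an eGFR of at least 30, so that 3.1.7 and 5.1 agree.

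Children keep the present rule.

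The cost is small, since the inputs are already collected. An occasional adult will start at half dose or be excluded under the existing Section 5.1 rule, which matters somewhat in a small pilot. A weight-free indexed eGFR will also flag fewer very small women than an unindexed clearance would (34.6 against 38.3 in the example shows the effect of indexing). That is the price of one simple, stated rule.
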